## **7.8 SAFETY ANALYSIS**

All safety analyses will be performed on the Treated Set.

### **7.8.1 Adverse events**

Unless otherwise specified, the analyses of adverse events will be descriptive in nature and will be based on BI standards (2). All analyses of AEs will be based on the number of patients with AEs and NOT on the number of AEs.

Furthermore, for analysis of AE attributes such as duration, severity, etc. multiple AE occurrence data on the CRF, will be collapsed into AE episodes provided that all of the following applies:

- The same MedDRA lowest level term was reported for the occurrences
- The occurrences were time-overlapping or time-adjacent (time-adjacency of 2 occurrences is given if the second occurrence started on the same day or on the day after the end of the first occurrence)
- Treatment did not change between the onset of the occurrences OR treatment changed between the onset of the occurrences, but no deterioration was observed for the later occurrence

The analysis of adverse events will be based on the concept of treatment emergent adverse events. That means that all adverse events occurring between first drug intake in 1199.33 until 28 days after last drug intake in 1199.33 will be assigned to the on-treatment period and described according to randomised treatment in parent trial. All adverse events occurring before first drug intake in 1199.33 will be assigned to 'screening' and all adverse events occurring after last drug intake + 28 days will be assigned to 'post-treatment', 'post-study' or 'follow-up' (for listings only). Some queries will be edited in case some adverse events are incorrectly reported in 1199.33 instead of parent trial, in order to report these in parent trial instead (before parent trial DBL). Also, all adverse events occurring between the start of an interruption and the end of interruption will be assigned to 'off-treatment' period in the listings. For details on the treatment definition, see [Section 6.1](#).

According to ICH E3 (3), AEs classified as 'other significant' will include those non-serious and non-significant adverse events with

- (i) 'action taken = discontinuation' or 'action taken = reduced', or
- (ii) marked haematological and other lab abnormalities or lead to significant concomitant therapy as identified by the Clinical Monitor/Investigator at a Blinded Report Planning Meeting.

An overall summary of adverse events will be presented.

The frequency of patients with adverse events will be summarised by randomised treatment in parent trial, primary system organ class and preferred term. Separate tables will be provided for patients with other significant adverse events according to ICH E3 (3), for

patients with serious adverse events, for patients with adverse events occurring with an incidence in preferred term greater than 5% (in at least one treatment arm), for patients with protocol specified significant adverse events (as ticked in the AE page of the CRF), for patients with related adverse events, for patients with adverse events leading to dose reduction and for patients with adverse events leading to treatment discontinuation.

The system organ classes will be sorted according to the standard sort order specified by EMA, preferred terms will be sorted by descending frequency over the total column (within system organ class).

Specific tables will be created in order to describe selected adverse events of particular note, such as diarrhoea events:

- Display of the diarrhoea specific page of the CRF
- Summary of diarrhoea events including time to onset, number and duration of episodes
- Summary of diarrhoea adverse events including seriousness, clinical consequences (dose -reduction, drug discontinuation or drug interruption) and outcome
- Kaplan-Meier plots of time to first diarrhoea event, by randomised treatment in parent trial and overall

Specific summary tables including seriousness, clinical consequences and outcome will also be presented to describe the following adverse events of particular note: nausea, vomiting, dehydration and weight decrease adverse events. Depending on the number of patients having such adverse events, summary tables including time to onset, number of episodes and duration together with Kaplan-Meier plots of time to first event, by randomised treatment in parent trial and overall, may also be produced with and without a y-axis cut-off at 70%.

Topics or syndromes that are medically relevant to the clinical development program are specified in [Table 7.8.1: 1](#). The frequency of patients with AEs within these topics or syndromes will be summarised by treatment, topic or syndrome and preferred term. A separate table will be provided for patients with serious AEs (SAEs), by treatment, topic or syndrome and preferred term.

Table 7.8.1:1 Aggregated adverse events by topic or syndrome

Organ system	Topic or Syndrome	Term selection
Gastrointestinal disorders		
	Pancreatitis	SMQ Acute pancreatitis
	Perforation	SMQ Gastrointestinal perforation (narrow)
Hepatobiliary disorders		

Table 7.8.1:1 Additional aggregated adverse events by topic or syndrome (cont'd)

	Liver enzyme and bilirubin elevations	SMQ Drug related hepatic disorders – comprehensive search (narrow); SMQ Liver related investigations, signs and symptoms (broad); SMQ Cholestasis and jaundice of hepatic origin (narrow); SMQ Hepatitis, non-infectious (narrow).
	Hepatic injury	SMQ Hepatic failure, fibrosis and cirrhosis and other liver damage-related conditions (narrow)
Vascular disorders		
	Bleeding	SMQ Haemorrhage terms (excl laboratory terms) (narrow)
	Venous thromboembolism	SMQ Embolic and thrombotic events, venous (narrow)
	Arterial thromboembolism	SMQ Embolic and thrombotic events, arterial (narrow); SMQ Myocardial infarction (narrow).
	Stroke	SMQ Ischaemic central nervous system vascular conditions (narrow); SMQ Haemorrhagic central nervous system vascular conditions (narrow).
Cardiac disorders		
	Cardiac failure	SMQ Cardiac failure (narrow)
	QT prolongation	SMQ Torsade de pointes/QT prolongation (narrow)
	MACE	
Renal disorders		
	Renal failure	SMQ Acute renal failure (narrow)

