4.2.1.1 Management of diarrhoea

The guidelines for managing diarrhoea are the same as in the parent protocols.

4-6 extra stools or i.v. fluid intake < 24 hours with no effect on daily living activities

Patients should be treated according to local standard (e.g. loperamide or equivalent).

If the severity of diarrhoea persists for 8 or more consecutive days despite optimal care, nintedanib treatment should be discontinued or reduced until return to less than 4 extra stools per day. Drug interruption is limited however to a maximum of 4 weeks and patients may restart treatment with nintedanib at a reduced dose (during a dose modification visit, refer to [Section 6.2.4](#)).

Dose re-escalation is allowed at any time after the beginning of the reduced dose if medically justified.

In case of re-occurrence of diarrhoea for 8 or more consecutive days despite dose reduction and after optimal or prophylactic therapy, patients have to permanently stop nintedanib and perform an End of Treatment Visit as soon as possible and a Follow-up Visit 28 days after last drug intake (refer to the [Flow Chart](#) for visit procedures).

> 6 extra stools or incontinence or i.v. fluid intake ≥ 24 hours or hospitalisation or decrease in daily living activities

Nintedanib has to be interrupted until return to less than 4 extra stools per day and patients should be treated with optimal supportive care (e.g. loperamide or equivalent). Thereafter, patients may restart treatment with nintedanib at a reduced dose.

In case of re-occurrence of diarrhoea for 8 or more consecutive days despite dose reduction and after optimal or prophylactic therapy, patients have to permanently stop nintedanib and perform an End of Treatment Visit as soon as possible and a Follow-up Visit 28 days after last drug intake (refer to the Flow Chart for visit procedures).

Proprietary confidential information.

© 2017 Boehringer Ingelheim International GmbH or one or more of its affiliated companies. All rights reserved.

This document may not - in full or in part - be passed on, reproduced, published or otherwise used without prior written permission.

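### The adverse event collapsing rule requires an identical MedDRA lowest level term, so one diarrhoea recorded under two such terms counts as two episodes in the planned episode summary

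*SAP*

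**What the plan says.** Under SAP 7.8.1, separate records of an event "will be collapsed into AE episodes provided that all of the following applies". The rule serves analyses of event attributes, duration and severity among them. The three conditions are:

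- term: "The same MedDRA lowest level term was reported for the occurrences";
- time: "The occurrences were time-overlapping or time-adjacent", where adjacent means that the second record starts on the day the first ends or on the day after;
- treatment, with deterioration judged on the later record: "Treatment did not change between the onset of the occurrences OR treatment changed between the onset of the occurrences, but no deterioration was observed".

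The same section summarises the frequency of patients with events by system organ class and preferred term. For diarrhoea it firmly plans a "Summary of diarrhoea events including time to onset, number and duration of episodes". For nausea, vomiting, dehydration and weight decrease, "summary tables including time to onset, number of episodes and duration together with Kaplan-Meier plots of time to first event" may be produced if enough patients have the event.

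SAP 7.8.1 also says that adverse event analyses count patients, not events. Protocol 7.2 describes all analyses as descriptive and exploratory.

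**The concern.** The rule builds episodes at one level of the dictionary, and the tables report at a coarser one. Several lowest level terms can sit under one preferred term. Because the conditions are joint, two diarrhoea records with different lowest level terms can never be merged, even if they touch or overlap in time. One patient can then have two simultaneous diarrhoea episodes, which is an artefact of coding.

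Diarrhoea is the drug's leading tolerability problem. Protocol 1.2 reports it in 61.5% and 63.2% of nintedanib patients in the parent trials, against 18.6% and 18.3% on placebo. A reader of the episode table will take an episode to be one continuous bout of diarrhoea. What is at stake is whether the reported number and duration of episodes carry that meaning.

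**Working it through.** The plan gives no figure on this point to reproduce, so the check applies the rule to simple examples.

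**Inputs**

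- Merging rule and planned output: SAP 7.8.1.
- True length of 12 days: assumed, for illustration.
- Share p of true episodes recorded under two lowest level terms: not in the documents; 5% to 30% assumed.

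**Step 1: one patient.** Two records have the same preferred term, and treatment does not change. They merge if the terms match at the chosen level and the second starts no later than the first one's end + 1 day. Duration = end − start + 1.

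| Records (days) | Lowest level terms | As written | By preferred term |
|---|---|---|---|
| 1–6 and 7–12 (adjacent) | different | 2 episodes: 6 and 6, mean 6.0 | 1 of 12 |
| 1–8 and 6–12 (overlapping) | different | 2 episodes: 8 and 7, mean 7.5 | 1 of 12 |
| 1–12 and 4–7 (nested) | different | 2 episodes: 12 and 4, mean 8.0 | 1 of 12 |
| 1–6 and 7–12 (adjacent) | same | 1 of 12 | 1 of 12 |

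The overlapping pair sums to 15 days, so 3 days are counted twice. The nested pair sums to 16, so 4 days are counted twice.

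**Step 2: the whole table.** Let x be the days counted twice in a split episode.

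- Episode count is multiplied by 1 + p.
- Mean duration = (12 + p·x)/(1 + p).
- For adjacent records x = 0, so mean duration falls by the fraction p/(1 + p).

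Adjacent records:

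| p | Episode count | Mean duration (days) | Fall |
|---|---|---|---|
| 5% | +5% | 12/1.05 = 11.4 | 4.8% |
| 10% | +10% | 12/1.10 = 10.9 | 9.1% |
| 20% | +20% | 12/1.20 = 10.0 | 16.7% |
| 30% | +30% | 12/1.30 = 9.2 | 23.1% |

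At p = 30% with the other two patterns:

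- overlapping, x = 3: (12 + 0.9)/1.30 = 9.9 days, a fall of 17.3%;
- nested, x = 4: (12 + 1.2)/1.30 = 10.2 days, a fall of 15.4%.

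The adjacent formula holds whatever the mix of true lengths, because total days do not change. The overlapping and nested figures assume that every true episode lasts 12 days.

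**Step 3: what does not move.** First onset is day 1 in every row of Step 1, so time to first diarrhoea is unchanged. A patient with one or two episodes is still one patient with diarrhoea, so incidence is unchanged. That includes the primary endpoint in Protocol 5.1.1.

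**The case against.** The strongest reply is that this is the sponsor's standard rule applied to one descriptive table, and that the visible documents cannot show how often it bites.

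- **Unseen text.** SAP 7.8.1 relies on a company standard for adverse events, and parts of SAP Section 5 are not in the public version. A further rule there cannot be excluded. The SAP also displays a diarrhoea-specific CRF page without saying whether it feeds the episode counts. This stands as a limit, but the rule that is visible is explicit and has no exception.
- **Unknown frequency.** Protocol 5.3.7 asks for one onset and one end date per event, and nothing shows how often a single diarrhoea is entered under two terms. This stands; every percentage above depends on an assumed p.
- **Different purposes.** Merging at one level and tabulating patients at another is not a contradiction. This is fair for the incidence tables. It does not help a table whose unit is the episode.

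A reader might also infer more than the documents support:

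- **That long episodes are hidden from the protocol's 8-day diarrhoea rules.** Protocol 4.2.1.1 has a rule that begins "In case of re-occurrence of diarrhoea for 8 or more consecutive days despite dose reduction and after optimal or prophylactic therapy". It is applied at the site. Failure to discontinue when required is a protocol violation (SAP Table 6.2: 1, code C7), found by manual review of listings. Neither step uses the derived episodes, and no visible table counts episodes of 8 or more days.
- **That intensity results for the events of particular note are distorted.** None of the visible tables for those events reports intensity.
- **That any two wordings split an episode.** Wordings coded to the same lowest level term still merge.
- **That both resulting episodes are always shorter.** With nested records, one keeps its full length.

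**Conclusion.** The point holds as a small one. As written, SAP 7.8.1 requires adjacent or overlapping diarrhoea records with different lowest level terms to be counted as separate episodes. The count is pushed up by the share p. For adjacent splits, mean duration is pushed down by p/(1 + p), about 5% to 23% over an assumed p of 5% to 30%; the fall is smaller for overlapping or nested records. The conclusion assumes two records per split episode, no treatment change between them, and no overriding rule in the text that is not public.

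The firm target is the diarrhoea summary; the matching tables for the other four events are optional. No conclusion on the primary endpoint, on the percentage of patients with an event or on time to first diarrhoea depends on it, and no clinical management rule is in question.

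**What to change.** Add one sentence to SAP 7.8.1: for the summary of number and duration of diarrhoea episodes, and for the corresponding tables on nausea, vomiting, dehydration and weight decrease if they are produced, overlapping or adjacent occurrences are collapsed when they share the same preferred term or belong to a predefined term list for that event. The time and treatment conditions stay as they are, and the lowest-level-term rule stays for all other tables.

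The cost is one changed derivation and no new data. The downside is a second episode definition in the SAP that departs from the sponsor's standard, so these counts would not be directly comparable with parent-trial counts built on that standard. A footnote, or the standard version shown alongside, deals with this. Showing both versions would also reveal how often records split, which the documents do not say.

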## 7.8.2 Laboratory data

The analyses of laboratory data will be descriptive in nature and will be based on BI standards (4).

Specific tables will be presented to describe liver enzyme elevations as defined in [Section](#)

5.4.4:

- Summary table of liver enzyme elevation including time to first onset and number of episodes
- Kaplan-Meier plot of time to first liver enzyme elevation (if sufficient number of events). No statistical test will be performed.
- Summary table of individual maximum liver enzyme and bilirubin elevations
- Plot of timecourse profile of liver enzyme for patients having liver enzyme and bilirubin elevation

**7.8.3 Vital signs**

Only descriptive statistics are planned for this section of the report, including calculation of the change from baseline.

**7.8.4 ECG**

[figure not shown]
Not applicable (ECG findings are reported as adverse events).

[figure not shown]
**7.8.5 Others**

[figure not shown]
Not applicable.

## 10. HISTORY TABLE

This is a revised TSAP including the following modifications to the final TSAP

Table 10: 1 History table

Version	Date (DD-MMM-YY)	Author	Sections changed	Brief description of change
Final	14-June-13	[REDACTED]	None	This is the final TSAP without any modification
Revised	29-September-15	[REDACTED]	4	As the protocol has been revised, the term "On trial survival" has already been changed into "Time to death"
			5.2.2	In accordance with new SOP, endpoints are now classified as further endpoints and not as secondary endpoints anymore.
			[REDACTED]	[REDACTED]
			[REDACTED]	[REDACTED]
			[REDACTED]	[REDACTED]
			[REDACTED]	[REDACTED]
			6.2	Precision added for IPV A2.1
			6.6	A reference to the CTP has been added for the handling of missing data.
			7.5.2	In accordance with new SOP, endpoints are now classified as further endpoints and not as secondary endpoints anymore.
			[REDACTED]	[REDACTED]
			7.7, 7.8.1	Precision that KM plots will also be performed overall groups and with 70% cut-off for y-axis for AEs of particular note
			[REDACTED]	[REDACTED]
			General	Reference section numbers have been updated or removed due to new classification of endpoints and for consistency purposes with revised CTP based on Global amendment 2.

Table 10: 1 History table (cont'd)

Revised	19-September-16	[REDACTED]	6.3	The definition of the Treated Set has been updated in order to specify that the Treated Set only includes patients from parent trials 1199.32/34 (and not transitioned patients from study 1199.35).
				[REDACTED]
Revised	25-Jul-17	[REDACTED]	7.2	The definition of baseline therapies was clarified. A summary of post-study drug discontinuation therapies has been added in order to display the proportion of patients having taken commercial nintedanib after trial drug discontinuation.
			7.8	Some specific AE tables by Topic or syndrome were added, as judged medically relevant for the project.
				[REDACTED]
				[REDACTED]
